4.3.4 Follow-up

AMS and Toronto score data will be collected prospectively at subsequent routine clinic visits. Infants will be examined until 6 months of age or until a decision for surgery is made, then until 1 year of age depending on the infant's recovery. After 1 year of age the progression of clinic visits varies based on the severity of the child's injury, with planned study visits at 18 and 30 months of age (2.5 years of age/±3 mo), regardless of surgery decision (i.e., both cohorts will be followed).

4.3.5 Removal from study

Subjects will be dropped from the study if a readable MRI is not produced, even after multiple attempts.

4.3.6 Description of study treatments or exposures/predictors

The primary predictor is the MRI-based Shriners Radiological Score (SRS.) Each patient's MRI will be read by the local study neuroradiologist and given a score between 0 and 25. The secondary predictors are the specific neuroradiologist interpretations of the MRI at each level (for later comparison with intraoperative findings).

4.4 Subject Recruitment Plans and Consent Process

4.4.1 Waiver of HIPAA Authorization for Recruitment of Prospective Subjects

4.4.1.1 HIPAA authorization will be obtained at the time of informed consent. We are requesting a waiver of HIPAA authorization for recruitment of prospective subjects. The use of health information for screening purposes does not represent more than a minimal risk to privacy.

- 4.4.1.2 It would not be possible to conduct this study without access to PHI, because the research staff will need to identify appropriate candidates prior to contacting their respective families.
- 4.4.1.3 Data will be coded and stored in a secured locked office. PHI will not be reused or disclosed to any other person or entity, except as required by law or for authorized oversight of the research project. Any disseminated data will be aggregated and coded. PHI will be destroyed at the earliest opportunity but no sooner than 2 years from the completion of this study.
- 4.4.1.4 Only IRB approved research staff for this study and those authorized for oversight of the research project will have access to PHI.
- 4.4.1.5 We will screen the electronic medical record for appropriate candidates for this study. PHI that will be accessed are name, MRN, DOB, dates of clinic visits, and medical notes.

4.4.2 Recruitment

- 4.4.2.1 Patient recruitment will take place during regular clinic appointments at each center. Research staff (RS) at each site will screen clinic schedules for appropriate candidates and alert the surgeon prior to a candidate's visit. On the day of the clinic visit, the surgeon will introduce the study to the parents/legal guardian, including risks and benefits of study participation, and answer any questions. If the parents/legal guardians express interest in participating, the RS will provide additional information, answer any questions, and then go through the formal consent process and obtain signature(s). Child assent will not be required due to the age of the subjects. The family will be given a copy of the signed consent form for their records.
- 4.4.2.2 If patients will be seen for this first time between 28 days and 4 months of age, the RS will secure a time slot for the MRI scanner ahead of time so that the MRI can be performed on the same day as the clinic visit. In this way, the MRI scan will occur as soon as possible after enrollment into the study. Patients whose first visit occurs prior to the age of 28 days will complete the research MRI at their next regularly scheduled clinic visit or at another time of their choosing. A handout or email given to families will contain information and tips about the MRI so that families can plan for the extra time needed to complete the MRI.
- 4.4.2.3 To minimize patient/family burden, ensure a high rate of retention, and maximize the likelihood that complete data are collected for each patient, the study visit schedule will mimic a regular clinic visit schedule. The only deviation necessary would be to complete the research MRI.

4.4.3 Informed consent process

- 4.4.3.1 Informed Consent will be obtained from their legally authorized representative or guardian by study staff authorized to consent for this study.
- 4.4.3.2 The consent process will include a thorough discussion of all the elements outlined in the informed consent document, including but not limited to what is expected to happen during the study, risks and benefits of the planned assessments, and any possible alternatives.
- 4.4.3.3 Subjects and their guardians will be presented with a verbal introduction to the study. They will then review the consent document section by section with the research personnel. The research staff will state that participation in the study is voluntary and that their care will not be affected should they choose to not participate. They will also be told that they can withdraw from the study at any time.
- 4.4.3.4 Consent will be obtained in a private location.
- 4.4.3.5 The subject/parent or guardian will be provided with an ample amount of time to ask questions before making their decision through extensive discussion between the parent or guardian and the research staff. This discussion includes the subject or guardian summarizing study procedures in their own words to ensure their comprehension level is adequate.
- 4.4.3.6 Potential subjects may take as much time as they would like to consider their participation in the study.
- 4.4.3.7 Consent of subjects enrolled at SHCNC will be documented in OnCore. The original consent form at all sites will be stored in locked filing cabinets at each site that only the research staff has access to.
- 4.4.3.8 The subject/family will be given a copy of the signed consent form.

5.0 Subject Safety

5.1 Safety Assessment

This study does not include experimental procedures.

- 5.1.1 No toxicities, injuries, complications or significant risks are expected with activities other than nerve exploration. These activities, performed as part of standard clinical care, will not require reporting as a study AE. At SHCNC, all standard SHC policies will be followed to insure subject safety while participating in all study-related procedures.

5.2 Serious Adverse Event Reporting

- 5.2.1 Any Serious and Unexpected adverse event, and Grade III or above with a reported causality of “possible,” “probably,” or “likely” must be reported to the Study PI in an expedited method.

- 5.2.2 The PI will ensure that SHC Headquarters and all applicable regulatory organizations are notified per regulatory guidelines.
 - 5.2.2.1 Shriners Hospitals for Children must be notified of any Serious **and** Unexpected adverse event, via the OnCore reporting mechanism, within 10 days of occurrence.
- 5.2.3 Notifying participating investigators
 - 5.2.3.1 The study PI will notify all participating investigators of any reported SAE adverse event associated with the study.

6.0 Data Handling and Record Keeping

- 6.1 Data
 - Data collected will include demographic information, physical examinations, Toronto scores and AMS, MRI readings, and surgery information.
- 6.2 Data Storage
 - 6.2.1 The data collected for this study will be stored (during and after the study) in OnCORE® Enterprise Research System, SHC's clinical research data management system housed on SHC servers. Members of the research team will enter data into the SHC system with unique user IDs and passwords. During the analysis phase, all secure web-based information transmissions will be encrypted.
 - 6.2.2 Source documents will be stored in locked filing cabinets that only authorized personnel will be able to access.
- 6.3 Confidentiality and Security
 - 6.3.1 All study data will be stored on SHC authorized servers outlined in this protocol. All computer systems will require a password to gain access. Data will be coded which will not allow for identification of any individuals from the code. The code sheet will be stored separately from the data.
 - 6.3.2 Investigators, approved study staff, and appropriate organizations such as the sponsor, collaborators, government agencies, and IRB may review records for research, quality assurance, and data analysis.
 - 6.3.2.1 A limited data set from each site will be sent to Boston Children's Hospital for statistical analysis.
 - 6.3.3 In the event that a subject revokes authorization to collect or use PHI, the investigator, by regulation, retains the ability to use all information collected prior to the revocation of subject authorization. For subjects that have revoked authorization to collect or use PHI, attempts should be made to obtain permission to collect at least vital statistics (i.e. that the subject is alive) at the end of their scheduled study period.
- 6.4 Source Documentation
 - 6.4.1 Data from each measure will be recorded onto paper data collection sheets before electronic entry. During the study, these source documents will be

stored in locked filing cabinets that only the study team has access to and on encrypted, password protected computers. After the study, source document and study files will be archived in a locked secure environment.

6.5 Record Retention

- 6.5.1 Clinical research records at SHCNC will be retained per SHC Standard Operating procedure on *Clinical Research Records Retention*. Record retention at participating sites will follow their respective institutional guidelines.
- 6.5.2 Any finding that materially affect the safety and medical care of past subjects from this study will be reported to the IRB for 2 years after closure.

7.0 Quality Control and Quality Assurance

7.1 Subject Safety

Because there are no study initiated interventions, the risk to subjects' safety is minimal. No additional measures will be taken in regards to patient safety.

7.2 Quality Control

7.2.1 MRI

All participating neuroradiologists will evaluate and score the MRI for the patients who participated in the pilot study, to establish inter- and intra-rater reliability prior to reading MRIs for the study. The first two MRIs completed at each site will be de-identified to patient and site and will be distributed to and read by all 3 neuroradiologists.

7.2.2 Physical Exam Assessments

In order to standardize the AMS scoring, the lead occupational therapist will meet with the therapists at the other sites to ensure consistency of scoring. This meeting/training will ensure that all sites will be scoring in the same manner going forward.

7.3 Monitoring Plan

- 7.3.1 The individuals responsible for data safety and monitoring will be the PIs and Co-Investigators. There are no conflicts of interest to declare, as the investigators have no personal or financial interest in this study.
- 7.3.2 The PIs will assure that informed consent is obtained prior to performing any research procedures, that all subjects meet eligibility criteria, and that the study is conducted according to the IRB-approved research plan.
- 7.3.3 The PIs will complete yearly reports detailing the study progress and subject status, any adverse events and any protocol deviations. These items will be discussed at the investigator meetings. Data will be presented in a blinded manner for confidentiality. Protocol adherence will be monitored by the PIs and the Co-Investigators. Protocol deviations are reported to the IRB at the time of continuing review.

8.0 Statistical Considerations

8.1 Primary Study Endpoints

The primary endpoint is the surgeon's decision for or against surgery, typically made by 6 months of age. Surgeons will make their decision based on all available clinical data, including the MRI, but will be blinded to the neuroradiologist's scoring of the SRS and its components.

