4.2.3 Standardization of indications for surgery

Surgeons will adhere to standard indications for microsurgery in infants with BPBP. These are: 1) flail arm and Horner's syndrome 2) Toronto score less than 3.5, 3) failure to recover antigravity elbow flexion and/or antigravity shoulder abduction (AMS score for elbow flexion and/or abduction less than 5), 4) failure to bring the hand to the mouth (cookie test), or other clinical indication of lack of appropriate nerve recovery.

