4.3 Study Procedures

4.3.1 Study Visits

At the baseline visit, we will collect patient demographics, prenatal and perinatal history, as well as information on any concomitant birth injuries. A standardized physical examination will be conducted at the enrollment visit and all subsequent study visits, consisting of the Toronto Score and AMS score. The Narakas score and the MRI will take place at or around the time of enrollment into the study. At the time of the MRI scan, the neuroradiologist will document the status of each nerve root as normal, post-ganglionic rupture, or pre-ganglionic avulsion, in addition to calculating the numerical SRS. For those infants who undergo microsurgery, we will document the indications for surgery, operative findings at each nerve root, and procedure performed at each nerve root.

[figure not shown]

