Each subject's MRI scan will be reviewed independently by neuroradiologist investigators. The neuroradiologists will interpret the MRI scan and report their findings in the medical record as per standard clinical protocols. Surgeons and families will be aware of these findings and will be able to view the images. However, the SRS calculation will be performed outside the medical record and will not be available to surgeons until after data collection is completed in order to minimize bias. Our pilot data demonstrated inter-rater reliability (Krippendorff's alpha) of 0.78 for calculation of the SRS. The neuroradiologist investigators at the other study centers will read and calculate SRS scores for the pilot study subjects with the goal of exceeding an inter-rater reliability of 0.75 with the other neuroradiologists prior to testing study subjects. In addition, during the study period, a subset of MRI scans will be de-identified and shared between institutions for the purposes of inter-observer and intra-observer analysis. Figure 1 illustrates the calculation of the SRS score from the MRI findings. Each injured level is first assigned 1 point, with additional points assigned for pre-ganglionic injuries: 2 points for each absent nerve rootlet, 2 points for each pseudomeningocele, 0.5 points for each abnormal nerve rootlet; and for post-ganglionic injuries: 1.5 points for each neuroma and 0.5 points for each abnormal nerve. If the zone of injury includes both the pre- and post-ganglionic regions, only the pre-ganglionic injury is scored. The total radiologic score ranges from 0 points (no evidence of nerve root injury on MRI) to 25 points (all 5 levels with pre-ganglionic pseudomeningoceles and absent nerve rootlets). In addition, the neuroradiologist will score each nerve root level as intact, post-ganglionic rupture, or pre-ganglionic avulsion. This information will then be compared with the findings at surgery as described above for those infants who undergo surgery.

Figure 1. Calculation of the Shriners Radiological Score (SRS)

4.3.2.1 Subjects who do not complete the scan or end up with unusable images can repeat the MRI up to two additional times as long as they are within the eligibility window.

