4.3.3 Surgery

The decision to proceed to surgery will be made by the operating surgeon using the accepted standard clinical indications. These are: 1) flail arm and Horner's syndrome 2) Toronto score less than 3.5, 3) failure to recover antigravity elbow flexion and/or antigravity shoulder abduction (AMS score for elbow flexion and/or abduction less than 5), 4) failure to bring the hand to the mouth (cookie test), or other clinical indication of lack of appropriate nerve recovery. For those infants in the study who undergo microsurgical plexus exploration, the status of each nerve root will be recorded by the operating surgeon as intact, postganglionic rupture, or pre-ganglionic avulsion. This status will be determined based on the intraoperative appearance of the nerve root as well as intraoperative SSEP testing as follows: avulsed (no repeatable response with maximal stimulation), ruptured (repeatable response to SSEPs but without distal motor function), or intact (repeatable response to SSEPs with distal motor function).

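### The primary AUC is open to partial incorporation bias of unknown, possibly small, size, and 8.4 plans no check of how sensitive it is to the MRI-informed decision

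*Combined protocol and SAP*

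**What the plan says.** All references are to the combined protocol and SAP.

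- **Reference.** Section 8.1 makes the surgeon's decision for or against surgery the primary endpoint and says of it: "Surgeons will make their decision based on all available clinical data, including the MRI". The same sentence blinds surgeons to the scoring of the SRS and its components.
- **What surgeons see.** Section 4.3.2: "The neuroradiologists will interpret the MRI scan and report their findings in the medical record as per standard clinical protocols". It continues: "Surgeons and families will be aware of these findings and will be able to view the images". The SRS itself is calculated outside the record and withheld until data collection ends (also 4.2.2).
- **Index test.** Under 4.3.6 each scan "will be read by the local study neuroradiologist and given a score between 0 and 25".
- **Basis of the decision.** Section 4.2.3: "Surgeons will adhere to standard indications for microsurgery in infants with BPBP". The listed indications there and in 4.3.3 are clinical and none names the MRI. The list ends "or other clinical indication of lack of appropriate nerve recovery".
- **Analysis.** Section 8.4 estimates the AUC of the SRS against going on to surgery, with a 95% CI. It allows an optional comparison with the AUC of the AMS. It uses AMS and Toronto scores at 18 and 30 months to confirm recovery in unoperated infants and to compare them with the surgery group.

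**The concern.** When the test under study feeds into the reference it is judged against, the two agree partly by construction. Here the number is hidden, but what it is built from is not: 4.3.2 scores absent or abnormal rootlets, pseudomeningoceles, neuromas and abnormal nerves, all read from images open to the surgeon.

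The objective in 2.1.1 concerns infants who need reconstruction versus those who recover on their own. The analysis in 8.4 concerns who was operated on. To the extent that the MRI moved decisions, these differ, and a high AUC supports only the second statement. Nothing planned would show how far the two diverge.

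**Working it through.** **1. The plan's own figure.** Section 8.3 gives 70 subjects for AUC 0.90 against a null of 0.75, with 30% surgical, 80% power and 5% type I error. The Hanley-McNeil large-sample variance, with k = non-surgical/surgical = 0.70/0.30 = 2.333, is

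V(A) = [A/(2-A) - A²]/k + [2A²/(1+A) - A²].

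This gives V(0.75) = 0.0964 and V(0.90) = 0.0461. Then

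n(surgical) = [1.645√0.0964 + 0.842√0.0461]² / 0.15² = 21.26, and the total is 21.26/0.30 = 70.9.

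This agrees with 70 using a one-sided 5% level. The plan does not state sidedness, which is a separate matter. The same variance is used for precision in step 4.

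**2. The passages side by side.**

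| Question | Answer in the plan |
|---|---|
| Does the decision use the MRI? | Yes (8.1) |
| Can surgeons see the report and images? | Yes (4.3.2) |
| Is the SRS scored from that scan? | Yes (4.3.2, 4.3.6) |
| Is the SRS withheld? | Yes, with the scoring of its components (4.2.2, 4.3.2, 8.1) |
| Do the listed indications name the MRI? | No, but the last item is open (4.2.3, 4.3.3) |
| Is there an SRS AUC against a reference not set by that decision? | No (8.4) |

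The two nearest checks do not fill the gap. The AMS AUC is a rival predictor, not another reference for the SRS. The 18- and 30-month scores do not enter an AUC, and they cannot show whether an operated infant would have recovered without surgery.

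**3. Possible size.** The documents give no weight for the MRI, so the bias cannot be calculated from them. As an illustration on assumed inputs, I simulated 1,000,000 infants with 30% surgical and a binormal SRS. With probability p the label follows whether the surgeon's own MRI reading falls in the top 30%. Either the reading replaces the examination-based label, or it can only add surgeries. The reading's within-class correlation with the SRS (rho) runs from 0.6 to 1.0. True AUC means the AUC against the decision made without the MRI.

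| True AUC | Apparent AUC, p = 20% | Apparent AUC, p = 40% |
|---|---|---|
| 0.75 (plan's null) | 0.76-0.80 | 0.77-0.85 |
| 0.85 | 0.85-0.88 | 0.85-0.91 |
| 0.90 (plan's target) | 0.90-0.92 | 0.90-0.94 |

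The upper ends need rho = 1 and full replacement. At true AUC 0.75 with rho 0.8 and replacement, the values are 0.782 and 0.814. At 0.90 with rho 0.6 the shift is slightly negative (lowest values 0.898 and 0.897). Few labels need to change: at true AUC 0.75, 2.8-5.5% for p = 20% and 5.5-11.1% for p = 40%, which is about 2-4 and 4-8 of 70 infants.

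**4. What a sensitivity AUC could resolve.** With 21 surgical and 49 non-surgical infants at AUC 0.90,

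SE² = [0.09 + 20(0.00818) + 48(0.04263)] / (21 × 49) = 2.300/1029 = 0.00224,

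so SE = 0.047 and the 95% half-width is 1.96 × 0.047, about 0.09. For the paired difference (20,000 simulated studies of 70 infants, true AUC 0.75), the mean gap is 0.008-0.050 with half-width 0.042-0.066 at p = 20%, and 0.017-0.100 with half-width 0.058-0.094 at p = 40%. A gap can also arise without any MRI influence: if the two references disagree at random in 5% of infants, an AUC of 0.90 against the first becomes 0.853 against the second.

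**The case against.** The plan discloses the MRI's role and acts on it. It withholds the SRS expressly to limit bias, blinds surgeons to its components as scored, and binds them to clinical indications. Even the open item is still a clinical sign of poor nerve recovery. The shares of 20% and 40% have no source in the documents, and the highest figures need the surgeon's unscored reading to rank infants exactly as the SRS does and to override the examination. At the plan's target of 0.90 the inflation is at most 0.04. If the MRI makes decisions more accurate, part of any rise is not bias.

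All of this stands, and it keeps the point modest. It does not remove it, because 8.1 says in terms that the decision uses the MRI.

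Three stronger readings are tempting, and the documents do not support them:

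- *That 4.2.3/4.3.3 and 8.1 contradict each other.* They describe the basis of the decision at different breadth, and the open item may bridge them. They need reconciling.
- *That the AUC will be materially inflated, or a poor score passed as a good one.* No passage says how much the MRI weighs, and 8.4 sets no pass rule against 0.75; it estimates an AUC with a CI.
- *That the blinding is void.* It removes the score and the scoring of its components. It leaves the report and images.

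**Conclusion.** The point holds as a limit on interpretation. Test and reference share a source by the plan's own statement, the safeguards reduce the dependence without removing it, and 8.4 has no analysis that would show how sensitive the AUC is to it. The size is unknown. Under the assumed mechanism it runs from about zero to 0.10 at a true AUC of 0.75 (0.85 - 0.75, in the extreme 40% case) and to 0.04 at 0.90. Those figures rest on the assumed shares, the binormal score and the chosen correlations, not on anything in the documents. Severity: consider. It is a cheap improvement and gives no reason to change the primary endpoint.

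**What to change.** Keep the surgical decision as the primary endpoint.

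1. **Add one supportive, ungated sensitivity AUC to 8.4**: the SRS against the protocol's own Toronto and AMS thresholds only. Section 4.3.1 collects these scores in every infant: "A standardized physical examination will be conducted at the enrollment visit and all subsequent study visits, consisting of the Toronto Score and AMS score". Leave out flail arm/Horner's, the cookie test and the open item. Section 4.3.1 promises a record of indications for operated infants only ("For those infants who undergo microsurgery, we will document the indications for surgery"), so recording of these items could follow the label.
   - Fix one analysis visit for all infants before analysis, for example the visit nearest a single pre-set age, or the last pre-decision examination if the decision came earlier.
   - Report the AUC with its 95% CI and the paired difference from the primary AUC.
   - State that examiners are not described as blinded to the MRI, that precision is low, and that a gap does not prove bias.
   - Do not use this reference for the SRS-versus-AMS comparison, which would be circular.
2. **Report how many operated infants had only the open-ended indication.**
3. **Word the primary conclusion** as discrimination of infants who did or did not go on to surgery, and give the MRI-informed reference as a limitation. Attach no CI criterion to this wording; the supportive AUC is too imprecise to act as a gate.
4. **Reconcile 4.2.3 and 4.3.3 with 8.1** on the basis of the decision.

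Cost: some protocol and SAP wording, one count, and one extra AUC on data already planned. Care and enrolment do not change. The downside is an imprecise second estimate, which will not resolve small gaps, and a slightly narrower headline.
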